3.13 Exit Interview

At the end of the week 12 testing visit, we conduct an exit interview to assess participants' satisfaction with the intervention and their perceptions of fruit. Specifically, we ask participants about any challenges they faced in adjusting to eating a high-fruit diet, their beliefs about the healthfulness of fruit, and for their feedback on the menu, the amount of fruit provided, and the study overall.

3.14 Potential Exploratory Analyses

We are collecting whole blood at weeks 0, 4, and 12 for potential future analyses of wholetranscriptome gene expression and/or epigenetic changes in peripheral blood mononuclear cells (PBMCs), pending available funding. In brief, whole blood is collected and transferred into Leucosep tubes containing Lymphoprep reagent (StemCell Technologies Inc.; Cambridge, MA), following the manufacturer's instructions. The resultant solution is centrifuged at 1000-1200 g for 12 minutes with the brake on. The mononucleocyte layer is then harvested into a new Leucosep tube and centrifuged at 400 g for 6 minutes. Most of the supernatant is discarded, and the white pellet is resuspended in the remaining 1-2 mL of supernatant. After determining cell density, the solution is centrifuged again at 400 for six minutes, and the remaining supernatant is discarded. The pellet is then resuspended using Invitrogen[™] RNAlater[™] (Life Technologies Corporation; Carlsbad, CA) and frozen at -80°C for potential future analysis.

At weeks 0, 4, and 12, we are also collecting stool samples for potential future analyses following the protocol described by Kumar et al.²⁰ Briefly, participants wipe their anus with a pre-moistened wipe immediately following a bowel movement on two separate occasions no more than 1-5 days apart. Participants temporarily store the wipes in a zip-lock bag in their freezer. On the day of the testing visit, participants bring in both samples, which are stored at -80 °C until future analysis.

4. Data Management and Statistical Methods

4.1 Data Management

Study data and questionnaires are collected and managed using REDCap electronic data capture tools hosted at UAB.^{21,22} REDCap (Research Electronic Data Capture) is a secure, web-based software platform designed to support data capture for research studies, providing (1) an intuitive interface for validated data capture, (2) audit trails for tracking data manipulation and export procedures, (3) automated export procedures for seamless data downloads to common statistical packages, and (4) procedures for data integration and interoperability with external sources. CGM data are uploaded and stored securely in the Dexcom Clarity® app (DexCom, Inc.; San Diego, CA).

4.2 Blinding

By necessity, participants and intervention staff are unblinded. Nursing staff unaffiliated with the study assess blood pressure and heart rate and perform the OGTTs blinded. Laboratory

technicians unaffiliated with the trial conduct the biochemical assays. MRI image analysis will be performed blinded. Data will be cleaned blinded by aggregating all time points together and/or by scrambling the order of timepoints.

4.3 Power Calculation

As this is a pilot and feasibility trial, the sample size was not based on a power calculation. We selected a sample size of 16 completers to provide sufficient data to inform the design of a future trial. Nonetheless, our study has 81% power to detect an 18.0% rate of attaining non-diabetic glycemia vs. a spontaneous remission rate of 0.7%.²³ Further, 16 completers provides 80% power to detect effect sizes of Cohen's d ≥ 0.78 , using a two-tailed paired t-test with α =0.05. This corresponds to a large effect size, which we expect, as participants eat a very large amount of fruit. We acknowledge that we are not powered to detect medium or small effect sizes, which may also be clinically relevant.

4.4 Statistical Analyses

All statistical tests will be two-sided with a Type I error rate of α =0.05. Because this is a controlled-feeding trial—designed to determine the cardiometabolic effects under conditions of nearly perfect adherence—we will analyze the data per protocol in completers only. The primary comparison will be between weeks 0 and 12, with secondary comparisons between weeks 0 and 4 and between weeks 4 and 12. Data may be Winsorized if there are outliers with an overwhelming degree of influence or values that are non-physiologic . We will test whether a fruit-rich diet can induce non-diabetic glycemia without hyperglycemia medications by testing whether our observed "remission" rate differs from the spontaneous T2D remission rate of

0.07% using an exact binomial test.²³ If there is one or more cases of non-diabetic glycemia, then the true rate is non-zero, and we will report a 95% confidence interval derived from bootstrapping. All other data will be analyzed as change scores. For all continuous data and Likert score data with at least four levels and sufficient variability, we will use linear mixed models with time as either a linear or categorical effect and with a random intercept for participants. For other data types, we will use distribution-appropriate generalized linear mixed models. Alternatively, if spline models are more parsimonious than treating time as a linear or categorical effect, we will use generalized-additive models with penalized adaptive regression splines instead. To analyze the data from CGM, we will perform a trajectory analysis to determine whether there are different "response phenotypes." Since it is conceivable that participants starting from very different baseline diets may have distinct trajectories early on, we may also consider a trajectory analysis of the data with special attention to the Ramp-Up phase and restrict the models to the Main Phase period after the trajectories converge. We will consider adjusting for covariates such as baseline values or mean 24-hour glucose levels only if statistically and clinically merited. For the inferential statistics on continuous variables, we will test for differences using least squares means evaluated at study timepoints, or alternatively, if time is most appropriately treated as a categorical variable, by the significance of the coefficient for each timepoint. We will analyze change in categorical variables using McNemar's test for dichotomous variables and Bowker's test of symmetry for variables with more categories. Finally, to assess inter-individual responses in the vein of precision nutrition, we will also report the percentages of participants who experience an improvement, no change, and a worsening in glycemic control.

5. Protocol Amendments

We made the following protocol amendments since recruitment began. First, the original menu designed for this trial was too challenging to consume due to its low energy density (3.14 kJ/g [0.75 kcal/g]). We revised the menu to be more energy dense (3.85 kJ/g [0.92 kcal/g]), and the new menu is described in this manuscript. Second, after the ADA released new guidelines defining T2D remission in August 2021, we immediately revised our definition of T2D remission to be consistent with the new guidelines. Third, to increase enrollment, we extended the age range from 20-65 years to 20-70 years and removed the lower limit on body mass index (BMI). We also added a criterion to exclude those unwilling to follow university mandates during the COVID-19 pandemic. Fourth, after discovering that participants ate healthier and/or substantially less food when they were filling out food records, we eliminated the food records during weeks 4 and 12 and move the baseline food record to be before CGM data collection started. Finally, as we were preparing this manuscript, we added a new statistician to our team ([name]) and revised the statistical analysis plan to fill in any gaps and be more detailed. At the time we made the last two decisions, [name], [name], and [name] had viewed safety data, medication data, and HbA1c data from the first three completers, and [name] had additionally viewed blood pressure, heart rate, and lipid data.

References

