1.5 Participants

We will enroll 16 adults recently diagnosed with insulin-independent T2D. We modeled our eligibility criteria on the landmark DiRECT study, which found that a VLCD intervention induces T2D remission in 46% of patients [3]. Like the DiRECT study, we are recruiting adults with insulin-independent T2D who were diagnosed with T2D within the past six years, as patients with diabetes durations longer than 6–8 years are less likely to achieve remission.² Table S1 in the appendix shows the eligibility criteria. To be eligible, applicants must have an HbA1c between 6.0–9.5%, be aged 20–70 years, and have a body mass index (BMI) \leq 45.0 kg/m². Key exclusion criteria include an estimated glomerular filtration rate (eGFR) <45 ml/min per 1.732 m², a change in body weight >5 kg in the past six months, a change in a chronic medication dosage that may affect study endpoints within the past three months, a significant health condition that might compromise the participant's safety or data validity, or inability to follow the study protocol. All participants must provide written informed consent prior to enrolling in the study. Participants are provided with a stipend, food, and a high-speed blender as compensation.

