2.7 Compliance

To ensure compliance during the controlled-feeding intervention, participants record themselves while preparing smoothies and eating all provided study food. We are using a previously validated method called remote video monitoring.⁴ In brief, we provide participants with an encrypted smartphone and tripod and teach them how to record themselves. Participants record themselves while eating all the provided food and preparing the smoothies. Research staff review the recorded videos for compliance and estimate the portion sizes of any uneaten food. We quantify compliance in based on the percent of the provided food calories consumed. Compliance rates below 80% or dishonesty are grounds for withdrawal.

3. Assessments

We will perform all assessments as detailed below.

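### The rate of non-diabetic glycemia without medication is planned in completers only, so any withdrawal would raise it above the rate among those who start; no rate over starters is planned

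*Combined protocol and SAP*

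**What the plan says.** Section 4.4 sets one analysis set for the whole trial: "we will analyze the data per protocol in completers only". The reason given is that the trial is "designed to determine the cardiometabolic effects under conditions of nearly perfect adherence". The rule covers level 1 of the primary hierarchy in section 1.3, the binary outcome of reaching non-diabetic glycemia off all antihyperglycemic medication. For that outcome the plan tests by exact binomial whether the observed "rate differs from the spontaneous T2D remission rate" and, if there is at least one case, reports a bootstrap 95% confidence interval.

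Section 2.7 states: "Compliance rates below 80% or dishonesty are grounds for withdrawal". Under section 3.2, planned cessation of medication comes at the end of week 10; before that, medication is changed only for safety concerns or adverse events. The primary comparison is week 0 against week 12.

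On numbers, section 4.3 says "We selected a sample size of 16 completers", while section 1.5 says "We will enroll 16 adults recently diagnosed with insulin-independent T2D". The two agree only if nobody leaves. No expected withdrawal rate is stated, and no rate over all who start, rule for counting non-completers, or sensitivity analysis is planned for the binary outcome.

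**The concern.** For a continuous change score, a completers set answers a clear question about physiology under adherence. A success proportion behaves differently. A participant on medication who leaves before the end of week 10 has normally had no chance to meet the off-medication criterion, so that person could not have been in the numerator. Removing the same person from the denominator can only raise the rate.

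Section 4.3 describes a pilot and feasibility trial whose sample size was chosen to inform a future trial. Planning that trial needs the proportion of people who begin the diet and then reach the outcome. If only the completer proportion is pre-specified, the reported figure is conditional on finishing 12 weeks of controlled feeding, and a reader may take it for the rate in those who start.

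**Working it through.** **Inputs from the documents.** Completers n = 16; power 81% for 18.0% against 0.7% (section 4.3). Two-sided α = 0.05, exact binomial test, completers only (section 4.4). Withdrawal proportion d: not given. Assumed range 10% to 40%.

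**Step 1: reproduce the stated power.** With n = 16 and a null rate of 0.7%, P(X ≥ 1) = 0.106, which is too large, and P(X ≥ 2) = 0.0055. The test therefore rejects at 2 or more achievers. Power = P(X ≥ 2 | 0.18) = 1 − 0.82^16 − 16 × 0.18 × 0.82^15 = 0.811. This matches the stated 81%, so that figure applies to 16 people who all complete.

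**Step 2: effect of the denominator on the rate.** Let k be the number of achievers, n the completers and N the starters, with N = n/(1−d) rounded up. If non-completers are not achievers, the completer rate is k/n, the starter rate is k/N, and their ratio is N/n, about 1/(1−d). Intervals are exact (Clopper-Pearson) 95%.

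| Assumed d | N | Ratio N/16 | 3 achievers: rate (95% CI) | 4 achievers: rate (95% CI) |
|---|---|---|---|---|
| 0 (completers) | 16 | 1.00 | 18.8% (4.0 to 45.6) | 25.0% (7.3 to 52.4) |
| 10% | 18 | 1.13 | 16.7% (3.6 to 41.4) | 22.2% (6.4 to 47.6) |
| 20% | 20 | 1.25 | 15.0% (3.2 to 37.9) | 20.0% (5.7 to 43.7) |
| 30% | 23 | 1.44 | 13.0% (2.8 to 33.6) | 17.4% (5.0 to 38.8) |
| 40% | 27 | 1.69 | 11.1% (2.4 to 29.2) | 14.8% (4.2 to 33.7) |

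If instead 16 is the number enrolled and 12 complete (d = 25%), 3 achievers are 3/12 = 25.0% of completers and 3/16 = 18.8% of starters.

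**Step 3: effect on the test.** Two achievers against 0.7% give p = 0.0055 at N = 16, 0.0070 at 18, 0.0086 at 20, 0.0112 at 23 and 0.0153 at 27. The p-value first exceeds 0.05 at N = 52 (0.0516). One achiever against 0.7% is not significant at any of these N (0.106 at 16, 0.173 at 27). Section 4.4 gives the null rate as 0.07% instead of 0.7%. That discrepancy is a separate point, but under 0.07% one achiever is significant throughout (0.011 at 16, 0.019 at 27). No test decision changes between 16 and 27 starters under either null.

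**Step 4: power of a test over all starters.** Suppose the true completer rate is 18%. If enrolment continues until 16 complete, power against 0.7% with all starters in the denominator stays at about 81% (81.4%, 80.5% and 80.5% at d = 10%, 20% and 30%). If only 16 are enrolled in total, it is 76%, 69% and 62%. The wording of sections 1.5 and 4.3 decides which case applies.

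**The case against.** The strongest reply is that the completers set is declared, justified and suited to the question. Section 1.1 asks whether remission is possible without weight loss, section 3.1 treats the outcome as a proxy for whether remission may be attainable, and section 4.4 limits the inference to near-perfect adherence. Counting people who did not eat the diet as failures answers a different question. This stands: the completer rate is valid for its own question and should be kept. It does not supply the figure that a feasibility trial needs for planning.

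It also stands that withdrawal below 80% compliance is permitted, not automatic, and that the screening interview (section 1.7) and the adherence-related exclusions in Table S1 should reduce attrition. With no withdrawals the two rates coincide. At the sizes in the table, the shift is small beside the width of the interval.

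A reader might infer four stronger things that the documents do not support.

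- That the comparison with the spontaneous rate is unfair because that rate has no adherence filter. The documents do not say how the rate was obtained or who was excluded from it.
- That participants leave because glucose worsens. Section 1.9 makes glucose values outside its limits grounds for considering medication changes; it does not mention withdrawal.
- That the amendment note saying "the original menu designed for this trial was too challenging to consume" (section 5) shows poor tolerance of the diet under test. It describes a menu since replaced by a more energy-dense one.
- That the result could not inform a future trial. A completer rate reported with the number of non-completers would let a reader derive the starters' rate. What the plan lacks is a commitment to report it.

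**Conclusion.** The point holds as a conditional one. Any withdrawal would raise the completer rate above the rate among starters by about 1/(1−d): 1.13 to 1.69 times for assumed withdrawal of 10% to 40%, or 18.8% against 16.7% to 11.1% with 3 achievers among 16 completers. The size in this trial cannot be known from the documents, because no withdrawal rate is given, and it is zero if nobody leaves.

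The direction assumes that non-completers are not achievers. The timing of planned cessation makes this reasonable for medicated participants. It is less secure for anyone taken off medication early for safety reasons.

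The consequence lies in the estimate and its interval. The exact binomial decision is the same at every N examined, so a claim that the test is materially biased would go too far. This is a worthwhile addition to the plan and does not invalidate the completers analysis.

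**What to change.** Keep the completers analysis as planned. Add one pre-specified analysis of level 1 to section 4.4: the proportion reaching non-diabetic glycemia without medication among everyone who starts the Ramp-Up Phase, with non-completers counted as not achieving. Report it with an exact (Clopper-Pearson) 95% interval beside the completer rate, and give the number of withdrawals and the reason for each. State in sections 1.5 and 4.3 whether 16 is the number enrolled or the number completing.

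The table of improvement, no change and worsening can stay on completers, since the plan has no rule for classifying people without week 12 data.

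The cost is one additional proportion and interval and a short account of withdrawals, with no new visits or measurements. The downside is a somewhat less favourable reported rate if anyone withdraws.

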1.8 Schedule of Assessments

Table S2 in the appendix shows the schedule of assessments. We measure all outcomes at week 0 (baseline), week 4 (end of the Ramp-Up Phase), and week 12 (end of the Main Phase). Most outcomes are assessed during a 4–5-hour testing visit, with the exception that CGM, stool collection (for exploratory analyses), and the abdominal MRI/S scans are conducted during the

week prior. Before each visit, participants fast for at least 10 hours. During each testing visit, we start by measuring anthropometrics, heart rate, and blood pressure. Thereafter, we collect a fasting blood draw and administer a three-hour OGTT. During the last hour of the OGTT, participants complete a series of questionnaires on food cravings, eating behaviors, mood, quality of life, and depression. Once the OGTT is complete, participants complete a Sweetness Taste Test. At week 12, we also conduct an exit interview.

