2.2 Ramp-Up Phase: Weeks 1–4

We give participants a four-week ramp-up period to acclimate to the high fiber and low energy density of the diet. The ramp-up period allows participants to adapt to eating low-energy-density food and overcome any transient gastrointestinal or bowel symptoms. The ramp-up period also provides preliminary data on the effects of whole fruit alone on cardiometabolic health before the remainder of participants' diet becomes a Mediterranean diet. During the ramp-up period, participants gradually eat more whole fruit as follows:

- Days 1-2: 10% of calories in the form of a frozen fruit smoothie;
- Days 3-7: 20% of calories in the form of a frozen fruit smoothie;
- Week 2: 30% of calories, with 25% as a smoothie and 5% as dried fruit;
- Week 3: 40% of calories, with 25% as a smoothie, 10% as dried fruit, and 5% as a fresh-fruit salad;

• Week 4: 50% of calories, with 25% as a smoothie, 12.5% as dried fruit, and 12.5% as a fresh-fruit salad.

To remain weight stable, participants are instructed to reduce their habitual diet in proportion to the amount of fruit added.

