2.3 Main Phase: Weeks 5–12

During weeks 5–12, participants consume a whole-fruit-rich diet that provides 50% of calories as whole fruit. The purpose of the main phase is to determine the effects of a whole fruit-rich diet while matching all aspects of the diet across participants, while also simultaneously maximizing the possibility that participants may be able wean off all their anti-hyperglycemic medications. The fruit composition of the diet is:

- Frozen fruit smoothie: 25% of calories;
- Fresh fruit salad: 12.5% of calories;
- Dried fruit: 12.5% of calories.

We deliberately include dried fruit and other fruits that do *not* have a low glycemic index, instead of only focusing on low-glycemic index fruits, to test fruits that are more representative of what people eat. Although most dried fruit has a moderate glycemic index, it does have a low glycemic load. During the Main Phase, the fruit smoothies also contain a small amount of other foods, such as a cup or two of leafy greens (green smoothies) and/or a couple tablespoons of flax or chia seeds. The remaining 50% of daily calories comes from Mediterranean-style diet. Participants must consume all the provided study food and only consume the provided food during the 12-week controlled-feeding intervention, except for two break meals per week. For the break meals, participants may substitute any meal of their choice for a non-fruit-containing study meal. Participants are permitted to drink zero-calorie beverages and add zero-calorie spices without salt to meals. Participants can eat study meals in any order as long as they consume either (a) the smoothie or (b) both the fresh salad and dried fruit by noon. We implemented this rule to help participants overcome the challenge of eating a low-energy-density diet by requiring participants to spread out their fruit consumption across the day. Additionally, participants must eat meals in one sitting, except for the fruit smoothies and fresh-fruit salads, which they can eat in two sittings. Finally, participants check off each study food item they eat or do not eat on a provided checklist. We also instruct participants to record any non-study food or beverage they consume on the food checklist.

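### The week 0–4 comparison, the only planned all-outcome contrast on fruit before the Mediterranean diet, drops anyone who leaves in weeks 5–12 even when their week-4 data are valid

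*Combined protocol and SAP*

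**What the plan says.** Section 4.4 states that "we will analyze the data per protocol in completers only". The reason given is that the trial is "designed to determine the cardiometabolic effects under conditions of nearly perfect adherence". The next sentence names the contrasts: "The primary comparison will be between weeks 0 and 12, with secondary comparisons between weeks 0 and 4 and between weeks 4 and 12". No contrast is given its own analysis set.

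The plan does not formally define a completer. Section 4.3 uses the word for the trial's sample size of 16, and sections 3.12 and 5 refer to the first three completers. In each place it reads as a person who finished the 12-week trial.

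Section 2.2 gives the week 0–4 data their own purpose. The ramp-up "provides preliminary data on the effects of whole fruit alone on cardiometabolic health before the remainder of participants' diet becomes a Mediterranean diet". From week 5 fruit is no longer isolated, because section 2.3 says: "The remaining 50% of daily calories comes from Mediterranean-style diet". Sections 1.4 and 1.8 place measurement of all outcomes at weeks 0, 4 and 12.

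Section 2.7 names compliance below 80% and dishonesty as grounds for withdrawal. Nothing in the document keeps week-4 data from a person who leaves in weeks 5–12. No sensitivity analysis in all participants with week-4 data is planned.

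**The concern.** Take a participant who eats the provided fruit through week 4, attends the full week-4 testing visit and leaves in week 6. Both measurements needed for the 0–4 contrast exist, yet the plan discards them because of something that happened later. The wish to estimate effects under near-perfect adherence can justify leaving people out of a period in which they did not adhere. It does not by itself justify leaving them out of an earlier period in which they did.

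Two things are at stake. The first is precision, in a trial that section 4.3 says is not powered for medium or small effects. The second is selection. An early estimate is conditioned on a later event, and that event may be related to tolerance or response. Section 5 reports that the first menu was too hard to consume, so exit because of burden is plausible. The contrast is secondary, but it is the planned source of information on fruit before the rest of the diet changes.

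**Working it through.** **Inputs from the documents**
- Sample size: 16 completers (section 4.3); 16 enrolled (section 1.5).
- Stated sensitivity: 80% power for d ≥ 0.78, two-tailed paired t-test, α = 0.05 (section 4.3).
- Dropout after week 4: not stated, so assumed below.

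**The plan's own figure.** With n pairs, the test statistic follows a non-central t distribution with n − 1 degrees of freedom and non-centrality d√n.
- n = 15, d = 0.78: power 80.2%.
- n = 16, d = 0.78: power 83.0%; the effect detectable at 80% power is d = 0.749.

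The stated 16 is thus reproduced to within one participant and is slightly conservative. The baseline used below is d = 0.75 at n = 16.

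**Scenario A: recruitment continues until 16 complete, and k = 2–5 others leave after week-4 testing (assumed).** The standard error with these people included, relative to completers only, is √(16/n).

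| n at week 4 | Detectable d (80% power) | SE ratio |
|---|---|---|
| 16 (completers only) | 0.749 | 1 |
| 18 | 0.701 | √(16/18) = 0.943 |
| 19 | 0.680 | √(16/19) = 0.918 |
| 20 | 0.660 | √(16/20) = 0.894 |
| 21 | 0.643 | √(16/21) = 0.873 |

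The standard error falls by 6–13%.

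**Scenario B: 16 are enrolled, all reach week 4, and 10–30% then leave (assumed).**

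| Leave after week 4 | Completers | Detectable d, completers only | Detectable d, all 16 |
|---|---|---|---|
| 10% | 16 × 0.9 = 14.4, about 14 | 0.81 | 0.75 |
| 20% | 16 × 0.8 = 12.8, about 13 | 0.85 | 0.75 |
| 30% | 16 × 0.7 = 11.2, about 11 | 0.94 | 0.75 |

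**Possible selection bias, sign left open.** The shift in the completers-only mean, relative to everyone with week-4 data, is the share who leave multiplied by the gap in mean 0–4 change between leavers and completers. At 20% leaving and a gap of 0.5 SD it is 0.20 × 0.5 = 0.10 SD. Over 10–30% leaving and gaps of 0.25–1 SD it runs from 0.10 × 0.25 = 0.025 SD to 0.30 × 1 = 0.30 SD. Both the gap and its sign are assumptions. The shift is zero if nobody leaves after week 4 or if leavers and completers changed alike.

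**The case against.** The strongest case for the plan is that one common set keeps the same people in all three contrasts, so that the 0–4 and 4–12 changes add up to the 0–12 change. That is a legitimate property, and the fix gives it up. The contrast is also secondary, section 2.2 itself calls the data preliminary, and the trial is an uncontrolled pilot in which fruit reaches 50% of calories only in week 4. Selection is unlikely to be the estimate's main limitation. These points limit the importance of the problem but do not remove it.

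Three stronger readings are tempting and are not supported.
- **That the bias favours the diet.** A reader might infer that leavers are those with poor glucose response. Section 2.7 gives only low compliance and dishonesty as withdrawal grounds, and section 1.9 links extreme glucose values to possible medication changes, not to withdrawal. A person who leaves because of food volume need not have had a worse change in glucose, liver fat or blood pressure.
- **That later conduct says nothing about weeks 1–4.** Dishonesty found in week 6 casts doubt on earlier records. Compliance is scored on provided food only, while the rest of the ramp-up diet is habitual food that participants reduce themselves. Adherence through week 4 can therefore be verified only for the fruit.
- **That these are the only data on fruit alone.** CGM, blood pressure, heart rate and lipids are also collected within weeks 1–4, and section 4.4 allows a CGM trajectory analysis with attention to the ramp-up. Those data fall under the same completers-only rule, and they do not cover all outcomes.

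**Conclusion.** The point holds as a matter of what the plan says: a later exit removes valid data from the 0–4 contrast, and the adherence rationale does not cover that in general. It rests on the ordinary meaning of a completer as someone who finishes week 12.

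Its size cannot be fixed from the documents. Under the assumed exits, the detectable effect improves from d = 0.75 to 0.70–0.64 (Scenario A), or is held at 0.75 instead of rising to 0.81–0.94 (Scenario B). Which scenario applies is unclear, because section 1.5 speaks of 16 enrolled and section 4.3 of 16 completers. Bias is possible, but its direction is unknown and may differ by outcome. The primary 0–12 comparison is not affected by this point. The change should be made, though the point does not threaten the trial's main conclusion.

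**What to change.** 1. Define a completer in section 4.4.
2. State the analysis set for each comparison. For weeks 0–4, use all participants with week-0 and week-4 data who met the existing provided-food compliance rule (section 2.7) in weeks 1–4, whether or not they finish week 12. Exclude anyone withdrawn for dishonesty.
3. Fit the 0–4 contrast as a separate model. Adding people with only weeks 0 and 4 to the planned three-timepoint mixed model would also alter the 0–12 and 4–12 estimates.
4. Keep the 0–12 and 4–12 analyses in completers as planned.
5. Report the 0–4 result in 12-week completers as a sensitivity analysis.

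No new data are needed, because week-4 testing is already scheduled for everyone. The cost is one extra model per outcome, and the 0–4 and 4–12 changes will no longer sum exactly to the 0–12 change. The completers-only sensitivity analysis restores that comparison on common participants for readers who want it.

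### The exact test of the remission outcome uses a null rate of 0.07% while the power statement uses 0.7%, and the difference decides whether 1 success in 16 is significant

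*Combined protocol and SAP*

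**What the plan says.** Achieving non-diabetic glycemia without antihyperglycemic medication is level 1 of the four-level hierarchy that defines the primary outcome, glycemic control (Section 1.3). Under that hierarchy a result at a higher level overrides those below it.

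- **Section 4.3 (Power Calculation):** "We selected a sample size of 16 completers", and "our study has 81% power to detect an 18.0% rate of attaining non-diabetic glycemia" when compared "vs. a spontaneous remission rate of 0.7"%. Reference 23 is cited.
- **Section 4.4 (Statistical Analyses):** the test asks whether the observed remission "rate differs from the spontaneous T2D remission rate of" "0.07% using an exact binomial test". Reference 23 is cited again.
- **Section 4.4, general rules:** "All statistical tests will be two-sided with a Type I error rate of" 0.05, and "we will analyze the data per protocol in completers only".

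Neither section mentions the other's figure, and the amendments listed in Section 5 do not explain the difference.

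**The concern.** The two sections give the same quantity, from the same source, with values ten-fold apart. In an exact one-sample binomial test the null rate sets the critical value. With 16 participants and a null close to zero, the critical value is 1 or 2, so the choice of null can change the rule itself.

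An analyst following Section 4.4 literally might declare level 1 significant on a single participant. An analyst using the planning rate in Section 4.3 might not. The stated power would then describe a different test from the one prespecified.

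**Working it through.** **Inputs.** n = 16 completers, alternative rate 18%, stated power 81% and null 0.7% (Section 4.3). Null 0.07%, exact binomial test, two-sided α = 0.05 (Section 4.4).

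**Formulas.** For X ~ Binomial(16, p):

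- P(X ≥ 1) = 1 − (1 − p)^16
- P(X ≥ 2) = 1 − (1 − p)^16 − 16·p·(1 − p)^15

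At both nulls zero successes is the most likely count. The two-sided p-value by the minimum-likelihood method therefore equals the upper tail. Doubled-tail values are shown as a check.

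**Step 1. Reproduce the stated power (null 0.7%).**

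- P(X ≥ 1 | 0.007) = 1 − 0.993^16 = 0.1063, above 0.05, so one success does not reject.
- P(X ≥ 2 | 0.007) = 0.1063 − 16 × 0.007 × 0.993^15 = 0.1063 − 0.1008 = 0.0055, so two successes reject.
- Power at 18% with at least 2 of 16: 1 − 0.82^16 − 16 × 0.18 × 0.82^15 = 1 − 0.0418 − 0.1468 = 0.8115.

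This matches the stated 81%.

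**Step 2. Repeat with the null in Section 4.4 (0.07%).**

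- P(X ≥ 1 | 0.0007) = 1 − 0.9993^16 = 0.0111, below 0.05, so one success rejects.
- Power at 18% with at least 1 of 16: 1 − 0.82^16 = 0.9582.

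**Step 3. Compare the decisions.**

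| Successes of 16 | p, null 0.7% (doubled tail) | p, null 0.07% (doubled tail) | Same decision? |
|---|---|---|---|
| 0 | 1 | 1 | Yes, not significant |
| 1 | 0.106 (0.213) | 0.011 (0.022) | **No** |
| 2 | 0.0055 (0.011) | 0.00006 (0.00012) | Yes, significant |

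Counts above 2 are significant under both nulls.

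**Step 4. Is the reversal sensitive to convention or to n?**

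- One success is significant only if the null is at or below 1 − 0.95^(1/16) = 0.32%, or 1 − 0.975^(1/16) = 0.16% with doubled tails. The two printed rates lie on opposite sides of both limits.
- For 12 to 20 completers, one success gives an upper-tail p of 0.081 to 0.131 against 0.7% and 0.008 to 0.014 against 0.07%.

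**Step 5. Error rate if the two rates are mixed.** If the true background rate is 0.7% and the test uses 0.07%, it rejects whenever X ≥ 1, so the false-positive rate is P(X ≥ 1 | 0.007) = 10.6%. For the 2-of-16 rule it is 0.55%. If 0.07% is the true background rate, the 1-of-16 rule has a type I error of 1.1%.

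**Step 6. How likely is exactly one success?** P(X = 1) = 16·p·(1 − p)^15. This is 14.7% at the planned 18%, 33% at 10% and 37% at 5%. The last two rates are illustrative assumptions.

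**The case against.** The strongest reply is that this is a decimal slip in a pilot. Section 4.3 says the sample size was not based on a power calculation, and the slip affects only one possible count. With no successes, or with two or more, the conclusion is the same under either null. That limit stands. But exactly one success is a realistic result in 16 people, and Section 4.4 still commits to a formal test at α = 0.05.

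Four further points are fair:

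- **The 81% does not prove 0.7%.** It needs only a critical value of 2, which holds for any null from about 0.32% to 2.27% (about 0.16% to 1.55% with doubled tails). It excludes 0.07%, and of the two printed rates only 0.7% yields it.
- **The 10.6% is conditional** on a true background rate of 0.7%. If 0.07% is correct, there is no inflation and the defect is a misstated power figure.
- **Level 1 is not the whole primary outcome.** Section 1.3 gives no trial-level rule that a significant level 1 makes the trial positive. It does let level 1 override the lower levels.
- **The p-value is not the only inference.** With one or more cases, Section 4.4 also treats the true rate as non-zero and reports a bootstrap confidence interval. A claim from a single case could be made under either null, but that does not settle which test result would be reported.

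**Conclusion.** The concern holds. The null rate is 0.7% in Section 4.3 and 0.07% in Section 4.4, from the same reference, and the test specified is not the test that was powered. At exactly 1 of 16 the level 1 result is significant as written (p = 0.011) and not significant at the planning rate (p = 0.106). Power at 18% is 81.1% under the planning rule and 95.8% under the rule in Section 4.4.

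This assumes 16 analysed completers and an exact two-sided test at 0.05. The reversal does not depend on which two-sided convention is used, and it persists for 12 to 20 completers. The documents alone do not show which rate is correct; the power figure favours 0.7%. The correction must be made before analysis, because it can reverse the significance of the highest-ranked primary measure.

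**What to change.** Check the spontaneous remission rate in reference 23, put that single value in Sections 4.3 and 4.4, and state the rejection rule and the two-sided convention.

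- **If 0.7% is confirmed:** correct Section 4.4 and state that at least 2 of 16 successes are required. The 81% power statement stands.
- **If 0.07% is confirmed:** correct Section 4.3. The rule is at least 1 of 16, with power of 95.8% at a true rate of 18%, or 80% at about 9.6% (1 − 0.2^(1/16) = 0.0957).
- **If the source gives another value:** recompute the critical value and power from the formulas above.

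Date and document the correction before level 1 is analysed. Section 5 records that the analysis plan was revised after some team members had seen medication and HbA1c data from the first three completers. This does not suggest that the rate was chosen from data, but a dated correction removes the question.

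The cost is one number and one sentence, with no change to sample size or conduct. If 0.7% is kept, a single success no longer counts as significant.
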